1.0 INTRODUCTION

This document is the clinical investigation plan (CIP) for the High Density (HD) Mapping Observational Study. This clinical study is a prospective, multi-center, single-arm, post-market observational study intended to quantify and characterize the outcomes of radiofrequency (RF) ablation after, and the utility of, electroanatomical mapping with the market-released HD mapping catheters Inquiry™ AFocusII™ Double Loop and Advisor™ HD Grid, Sensor Enabled™ with the EnSite Cardiac Mapping System and the Ensite Automap Module in subjects with atrial fibrillation in the real-world environment of the Asian population. This clinical study is sponsored by Abbott.

The clinical investigation will be conducted in accordance with this CIP. All investigators involved in the conduct of the clinical investigation will be qualified by education, training, or experience to perform their tasks and this training will be documented appropriately.

1.1 Background and Rationale

1.1.1 Background

Atrial Fibrillation (AF) is a supraventricular arrhythmia characterized by rapid and irregular activation in the atria. AF can be divided into two main types based on the frequency of occurrence: paroxysmal and persistent. Paroxysmal AF (PAF) is defined as AF that terminates spontaneously or with intervention within 7 days of onset. Persistent AF (PersAF) is defined as continuous AF that is sustained beyond 7 days.¹ AF is progressive from PAF to PersAF; disease progression is due to arrhythmia-induced tissue remodeling that results in changes in contractile properties, electrical properties, and tissue structure.² AF remains a major cause of stroke, heart failure, sudden death, and cardiovascular morbidity and is associated with increased rates of hospitalization.^{3, 4} Restoration and maintenance of sinus rhythm either thru pharmacological or non-pharmacological methods is the standard of treatment.⁵ Based on epidemiological studies of mainly North American and European populations, an estimated 20.9 million men and 12.6 million women suffer from AF.⁶ The prevalence of AF is lower in Asians than in Westerners and is estimated to be approximately 0.7-1.1% in Asians older than 40. Despite this apparent difference in prevalence, the burden of AF in the Asia Pacific region is expected to become far greater than that in Western regions based on the increasing age and size of populations within the Asia Pacific regions.^{7, 8}

Catheter ablation is an established treatment option for AF¹, although corresponding success rates in long-term sinus rhythm maintenance remain modest and could benefit from further research. Ablation strategies target the pathogenic mechanisms that initiate and perpetuate abnormal electrical activity within the heart including abnormal substrates. However, identifying and eliminating the pathogenic mechanisms is not straightforward, especially with complex arrhythmias in which the distribution of potential arrhythmogenic drivers is heterogeneous across the patient population and there remains a lack of consensus on approach to identifying and ablating mechanistic drivers.

AF is electrophysiologically characterized by fast and regular atrial activities, complex fractionated atrial electrograms, direction of wave front propagation, and low peak-to-peak voltage. Pulmonary veins are believed to be the primary trigger of AF. In cases of PersAF, triggers beyond pulmonary vein triggers may include areas of fibrosis, focal automaticity, or foci, areas of rapidly rotating reentrant circuits, or rotors, asynchronous activation of myocyte bundles identified by complex fractionated electrograms, overactive ganglionated plexi, and dissociation and interaction between epicardial and endocardial layers.^{1, 9, 10} The role of such mechanisms continues to be debated along with their implication on therapeutic strategy, especially since ablation techniques aim to eliminate AF triggers or modify arrhythmogenic substrate

Clinical Investigation Plan

Electroanatomical mapping (EAM) techniques are used to locate pathologic substrates that trigger arrhythmias including identification of local abnormal ventricular activities (LAVA), late potentials, fractionated electrogram signals, and activation mapping.^{11, 12} The effectiveness of catheter ablation relies heavily on the accuracy, resolution and fidelity of mapping results. Initially, EAM relied on point-to-point annotation with a single electrode unipolar or bipolar mapping catheter contacting tissue, resulting in limited quality maps. The point-by-point acquisition process is time consuming and may miss small areas critical to the aberrant circuit. The development of linear, multielectrode mapping catheters that contact tissue such as the Inquiry™ AFocusII™ Double Loop allow for more rapid collection of data resulting in high-density maps. Maps created with these catheters may be influenced by the direction of the wavefront, catheter orientation, electrode size, interelectrode spacing, proximity to tissue and contamination by far-field signals.¹² Accurate electrogram depiction of underlying substrate is limited by adequate bipole orientation which can be challenging to achieve with these traditional linear mapping catheters.¹³ Nonlinear, multielectrode, tissue contacting catheters were developed to help circumvent some of these limitations. For example, the Advisor™ HD Grid diagnostic mapping catheter was created with equi-spaced multipolar grid electrodes with known bipole spacing in orthogonal directions, thereby providing the ability to discriminate voltage differences in two directions for enhanced directionality and amplitude detection.

1.1.2 Rationale for Conducting this Clinical Investigation

EAM with HD mapping catheters has been shown to provide insight into the extent of structural disease and assist in the determination of the critical atrial targets to guide catheter ablation strategy. This allows physicians to avoid both unnecessary overtreatment that could result in increased risk of complication, procedure duration, and fluoroscopy exposure, as well as undertreatment with increased likelihood of recurrence in patients that present with complex arrhythmias. The utility of HD mapping catheters on the subsequent ablation strategies used by physicians and the outcomes of ablation would benefit from further study, particularly in the Asia Pacific region, where research in AF has been less prevalent.

2.0 CLINICAL INVESTIGATION OVERVIEW

2.1 Clinical Investigation Objective

The aim of this study is to quantify and characterize the outcomes of radiofrequency (RF) ablation after, and the utility of, electroanatomical mapping with the market-released HD mapping catheters Inquiry™ AFocusII™ Double Loop and Advisor™ HD Grid, Sensor Enabled™ with the EnSite Cardiac Mapping System and the EnSite Automap module in subjects with AF in the real-world environment of the Asian population.

This study is meant to serve as a post-market observational study. As such, no formal hypothesis testing will be performed. The objective of the study is to evaluate several procedural details related to HD mapping as well as the outcome of the radiofrequency (RF) ablation after electroanatomical mapping with HD mapping catheters.

2.2 Devices to Be Used in the Clinical Investigation

2.2.1 Names of the Devices Under Investigation

All devices used in this clinical study must have proper regulatory approval and will be used according to their indications for use and Instructions for Use (IFU)/Package Insert.

Clinical Investigation Plan

The devices that will be used in this clinical study are summarized in Table 1. Additional commercially available tools may be used in this clinical study, per physician’s discretion. All tools utilized must be done so according to the specific device indications for use and IFU/package insert.

Table 1. Clinical Study Devices

Device name	Model/Type	Manufacturer
EnSite Precision™ Cardiac Mapping System Software (SV 2.2 or later)	H702496	SJM
EnSite Velocity™ Cardiac Mapping System Software (SV 5.0 or later)**	H702495	SJM
Advisor™ HD Grid Mapping Catheter, Sensor Enabled™	D-AVHD-DF16	SJM
Advisor™ HD Grid Mapping Catheter, Sensor Enabled™ Software Kit (License entitlement to use HD Grid Catheter with EnSite Precision™ SV 2.2)	H702519	SJM
Sensor Enabled™ Diagnostic Catheter Cable	D-AVSE-CBL22	SJM
EnSite™ AutoMap Module	H702498	SJM
Inquiry™ AFocusII™ Double Loop Electrophysiology Catheter	IBI-87008	SJM
Inquiry™ AFocusII™ 24-Pin Diagnostic Connecting Cable	1924-S	SJM

** The EnSite Velocity™ Cardiac Mapping System may be available in other regions. For this clinical study, its use is restricted to China only.

2.2.2 Indication for Use

Indications for use may be found in the appropriate device IFU/Package Insert. Indications for the use of each of the HD mapping catheters and the specific EnSite Cardiac Mapping System are described below.

The Advisor™ HD Grid Mapping Catheter, Sensor Enabled™, is indicated for multiple electrode electrophysiological mapping of cardiac structures in the heart with recording or stimulation only. This catheter is intended to obtain electrograms in the atrial and ventricular regions of the heart.

The Inquiry™ AFocus™ catheters are for recording intracardiac signals and cardiac stimulation during diagnostic electrophysiological studies. The Inquiry™ AFocus™ catheters are for use in mapping atrial regions of the heart.

The EnSite Velocity™ Cardiac Mapping System is a catheter navigation and mapping system capable of displaying the three-dimensional (3D) position of conventional electrophysiology catheters, as well as displaying cardiac electrical activity as waveform traces and as dynamic 3-D isopotential maps of the cardiac chamber. The contoured surfaces of these three-dimensional maps are based on the anatomy of the patient’s own cardiac chamber. The EnSite Velocity™ Cardiac Mapping System (including AutoMap) is a suggested diagnostic tool in patients for whom electrophysiology studies have been indicated. When

Clinical Investigation Plan

used with an EnSite Velocity™ Surface Electrode Kit, the EnSite Velocity™ Cardiac Mapping System is intended to display the position of conventional electrophysiology (EP) catheters in the heart.

The EnSite Precision™ Cardiac Mapping System is a catheter navigation and mapping system capable of displaying the three-dimensional (3D) position of conventional and sensor enabled electrophysiology catheters, as well as displaying cardiac electrical activity as waveform traces and as dynamic 3D isopotential maps of the cardiac chamber. The contoured surfaces of these 3D maps are based on the anatomy of the patient's cardiac chamber. The EnSite Precision™ Cardiac Mapping System (including AutoMap) is a suggested diagnostic tool in patients for whom electrophysiology studies have been indicated. The EnSite Precision™ system interfaces to either MediGuide™ Guided Medical Positioning System or the EnSite Precision™ Module to combine and display magnetic processed patient positioning and orientation mapping information. When used with an EnSite Precision™ Surface Electrode Kit, the EnSite Precision™ Cardiac Mapping System is intended to display the position of conventional electrophysiology (EP) catheters in the heart.

2.2.3 Description of the Devices Under Investigation

Please refer to the IFU/Package Insert for additional information regarding the devices used in this clinical study, pictured in the following figures.

[figure not shown]

Figure 1. Inquiry™ AFocusII™ Double Loop Electrophysiology Catheter

Clinical Investigation Plan

[figure not shown]

Figure 2. Advisor™ HD Grid, Sensor Enabled™ Mapping Catheter

3.0 CLINICAL INVESTIGATION DESIGN

This is a prospective, non-randomized, multi-center, single-arm, post-market observational study to characterize the outcomes of RF ablation after, and the utility of, electroanatomical mapping with the market-released HD mapping catheters Inquiry™ AFocusII™ Double Loop and Advisor™ HD Grid Mapping Catheter, Sensor Enabled™ with the EnSite Cardiac Mapping System in subjects with AF in the real-world environment of the Asian population. Approximately 200 subjects will be enrolled at up to 20 investigational sites in the Asia Pacific (APAC) region.

3.1 Clinical Investigation Procedures and Follow-up Schedule

Subjects will be consented for the trial prior to any data collection. Once eligibility is confirmed and a subject is consented, baseline information will be collected and the subject will undergo the RF ablation procedure per physician discretion using electroanatomical mapping with either Inquiry™ AFocusII™ Double Loop or Advisor™ HD Grid, Sensor Enabled™ depending on market release in the specific region. Subjects will be followed for 12 months post procedure. Follow-up assessments will occur in person at a clinic. The study visits will occur at baseline, procedure, pre-discharge, 6 months post ablation procedure, and 12 months post ablation procedure. The subject will be exited from the study after completion of the 12-month follow-up visit. The visit schedule and related study assessments are summarized in Figure 4 and further detail is provided in Section 6.0.

Clinical Investigation Plan

[figure not shown]

Figure 3. Clinical Investigation Flow Chart

3.2 Measures Taken to Avoid and Minimize Bias

Multiple measures will be taken to avoid bias in this clinical study. First, the HD Mapping Study is prospective, such that the outcome of the study is unknown at time of enrollment, and all subjects must meet pre-defined eligibility criteria thereby minimizing selection bias. Next, guidance will be provided to sites regarding data collection for questionnaires and post-procedure follow-up visit. Case report forms for data collection will be provided to all sites thereby minimizing inter-observer variability. Evaluation of arrhythmia recurrence via Holter monitoring will be performed by an independent core laboratory. Additionally, protocols are in place to minimize subjects lost to follow-up and collection of missing data to minimize the impact or bias caused by missing data.

3.3 Suspension or Early Termination of the Clinical Investigation

While no formal statistical rule for early termination of the clinical investigation for insufficient effectiveness of the device under investigation is defined, the Sponsor reserves the right to discontinue the clinical

Clinical Investigation Plan

investigation at any stage or reduce the follow-up period with suitable written notice to the investigator. Possible reason(s) may include, but are not limited to:

- A new unreasonable risk to the participating subjects has been identified such as an unanticipated increase in complaint rates related to the study.

Should the clinical investigation be discontinued by the Sponsor, subjects will be followed per routine hospital practice with device-related adverse events (AEs) reported to the Sponsor as per vigilance/commercial reporting requirements. All applicable clinical investigation documents shall be subject to the same retention policy as detailed in Section 11.0 of the CIP.

A Principal Investigator, Ethics Committee (EC) or regulatory authority may suspend or prematurely terminate participation in the clinical investigation at the investigational site(s) for which they are responsible. The investigators will follow the requirements specified in the Clinical Trial Agreement.

If the Sponsor suspends or prematurely terminates the clinical investigation at an individual site in the interest of safety, the Sponsor will inform all other Principal Investigators.

4.0 **ENDPOINTS**

4.1 **Utility Endpoint**

The utility of HD Mapping catheters with the EnSite Cardiac Mapping System will be quantified and characterized through the summary of the following:

- Overall procedure time: defined as time from initial catheter insertion to final catheter removal.
- Radiofrequency (RF) time: defined as duration of time RF energy is delivered
- Fluoroscopy time: defined as total time subject is exposed to fluoroscopy
- Mapping time associated with mapping arrhythmia: defined as the total cumulative mapping time and mapping time for the creation of each map (including any new or retrospective map created with Manual, AutoMap, and TurboMap mapping)
- Number of mapping points collected: defined as total number of mapping points collected for the creation of each map
- Number of mapping points used: defined as the total number of mapping points used in each map
- Number of used mapping points per minute: defined as the total number of mapping points used divided by the relative mapping time
- Substrate characteristics identified: for each type of arrhythmogenic substrate this will be defined as the frequency of substrate type identified in cases that attempted to identify the specific substrate
- Ablation strategy(s) used: defined by both the type of map used to define ablation strategy and the frequency each ablation strategy/target was used by physicians

4.2 **Outcomes Endpoint**

To quantify and characterize the acute- and long-term success rate of RF ablation after electroanatomical mapping with HD mapping catheters, the following will be summarized:

- Rate of acute success defined as the proportion of subjects who receive HD mapping and RF energy delivery resulting in acute termination of clinical arrhythmia, defined by termination to SR

Clinical Investigation Plan

(or AT if being treated for PersAF) or non-inducibility of clinical arrhythmia after ablation (cardioversion allowed prior to inducibility attempt).

- Rate of long-term success defined as the proportion of subjects who receive HD mapping and RF energy delivery with the following pre-defined procedural endpoints:

AF (utilizing a 90-day blanking period following index ablation):

- freedom from all atrial arrhythmias (AF/AFL/AT) greater than 30 seconds (as documented by 24-hr Holter at 12-month follow-up) and on or off class I/III antiarrhythmic drug (AAD).
- freedom from all atrial arrhythmias (AF/AFL/AT) greater than 30 seconds (as documented by 24-hr Holter at 12-month follow-up) and off all class I/III AADs.

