6.3 Pre-discharge Visit (In-hospital)

6.3.1 Clinical Assessments

Prior to discharge after the study procedure, a Pre-discharge visit will be completed. The following information will be collected from each subject:

- Arrhythmia recurrence
 - For the purposes of this clinical study recurrence of arrhythmia is deemed to have occurred only when the arrhythmia is documented on ECG, or other monitoring device used per standard of care. Atrial arrhythmias 30 seconds or longer will be collected.
- Antiarrhythmic medications - any current class I/III AAD and dose
- Adverse events if applicable
- Protocol deviations if applicable

Clinical Investigation Plan

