7.3 Adverse Event Reporting

7.3.1 Adverse Event Reporting

Safety surveillance and reporting starts as soon as the patient is enrolled in the clinical investigation. Safety surveillance and reporting will continue until the last follow-up visit has been performed, the subject is deceased, the subject concludes participation in the clinical investigation or the subject

Clinical Investigation Plan

withdraws from the clinical investigation. Adverse event data, including deaths, will be collected throughout the time period defined above and will be reported to the Sponsor on a CRF. Additional information with regard to an adverse event should be updated within the appropriate CRF.

Unchanged, chronic, non-worsening or pre-existing conditions are not AEs and should not be reported.

An offline form will be made available to allow the investigator to report serious adverse events (SAEs) in the event the entry cannot be made in the EDC. This does not replace the EDC reporting system. All information must still be entered in the EDC system as soon as feasible.

Non-cardiac related abnormal laboratory values will not be considered AEs unless:

1. the investigator determined that the value is clinically significant,
2. the abnormal lab value required intervention, or
3. the abnormal lab value required subject withdrawal from the clinical investigation.

For the purposes of this clinical investigation, the following events will be reported:

- Adverse events that are considered related to either the ablation catheter or the ablation procedure by the investigator
- Adverse events resulting in death

Recurrence of AF, AFL, or AT are not considered reportable adverse events unless they occur in a severity, frequency, or other manner that is significantly worse than the subject's baseline condition. These are considered lack of effectiveness and will be reported as a recurrence on the appropriate case report form.

SAE Reporting

The investigator should report all SAEs to the Sponsor as soon as possible but no later than outlined below.

Clinical Site	Reporting timelines
All Sites	SAEs must be reported to the Sponsor no later than 3 calendar days from the day the site personnel became aware of the event or as per the investigative site's local requirements, if the requirement is more stringent than those outlined.

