8.2 Statistical Analysis

8.2.1 Characterization Endpoint Analysis

The endpoints will be summarized descriptively based on available data or measurements in the analysis population. No formal hypothesis testing will be performed.

In general, continuous variables will be summarized with the numbers of observations, means with standard deviations, minimums, and maximums as per the table mockups.

Categorical variables will be summarized with subject counts and percentages/rates, and where specified in the table mockups.

Survival analysis will be conducted to analyze time-to-event variables. Events occurring during the 90 days following the ablation procedure for AF subjects (90-day blanking period) will not be counted as an effectiveness outcome failure. Subjects without events will be censored at their last known event-free time

Clinical Investigation Plan

point. Subjects withdrawn or otherwise lost-to-follow-up during the follow-up period will be censored at their last known visit. Survival data will be presented using the Kaplan-Meier product limit method.

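### Long-term success rests on one 12-month Holter, with a 90-day blanking period that cannot affect it and a Kaplan-Meier event that the visible text does not name

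*Combined protocol and SAP*

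**What the plan says.** Section 4.2 (Outcomes Endpoint) gives two long-term success rates, one regardless of antiarrhythmic drug use and one "off all class I/III AADs". Both use the same rhythm criterion: "freedom from all atrial arrhythmias (AF/AFL/AT) greater than 30 seconds (as documented by 24-hr Holter at 12-month follow-up". Both stand under the lead-in "AF (utilizing a 90-day blanking period following index ablation". Appendix XII repeats this wording.

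Sections 6.4.1 and 6.6 schedule one Holter, at the 12-month visit (360 ± 14 days). Section 6.7 says the core laboratory's reading is what will be analysed, and Section 3.2 lists that independent reading among the measures against bias.

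Section 8.2.1 says that events within the "90-day blanking period) will not be counted as an effectiveness outcome failure". It plans survival analysis for time-to-event variables, which the visible text does not list, and adds "Survival data will be presented using the Kaplan-Meier product limit method".

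Two other sections touch on recurrence. Section 6.3.1 says that, for this study, "recurrence of arrhythmia is deemed to have occurred only when the arrhythmia is documented on ECG, or other monitoring device". Section 7.3.1 says of recurrent AF, AFL or AT: "These are considered lack of effectiveness and will be reported as a recurrence on the appropriate case report form".

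Repeat ablation is listed separately in Section 4.3, as the proportion *with* a further procedure outside the blanking period. Appendix XII defines the same rate as the proportion *without* one.

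**The concern.** The endpoint and the analysis section do not fit together. A blanking period has a purpose when events are counted over follow-up, because it removes the early ones. It has none for a single recording made near day 360. A Kaplan-Meier analysis with censoring likewise presupposes dated events spread over follow-up. If only the 12-month Holter counted, every event would fall at about the same time.

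Followed as written, Section 4.2 makes a long-term success of a subject with AF on an ECG at month 5, or a second ablation at month 7, whose 12-month Holter is clean.

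The study has no hypothesis tests and no pass/fail criterion, so no error rate is at stake. But quantifying the long-term success rate is a stated purpose, and in a descriptive study the definition determines the result. The study is unblinded, and Section 8.0 allows additional analyses during follow-up, so a definition left open could be settled with data in view.

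**Working it through.** The visible text gives no success rate, recurrence rate or precision target, so there is no plan figure to reproduce. The check has two parts.

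**Timing (figures from Sections 4.2 and 6.4.1).**
- Earliest Holter: 360 − 14 = day 346. Latest: 360 + 14 = day 374.
- Distance from the end of blanking: 346 − 90 = 256 days to 374 − 90 = 284 days.
- Share of the post-blanking time covered by a 24-hour recording: 1/284 = 0.35% to 1/256 = 0.39%.

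No blanked event can appear on this Holter, so the clause changes nothing under a Holter-only reading.

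**Size (all inputs assumed).** Take the same subjects, complete Holters and simple proportions. Let r be the share with any arrhythmia documented after day 90, the 12-month Holter included as a source. Let q be the share of those who are positive on that Holter.
- Holter-only success = 1 − rq
- Freedom from any documented recurrence = 1 − r
- Gap = (1 − rq) − (1 − r) = r(1 − q), which is never negative

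Example with 200 subjects, r = 30%, q = 0.7: 60 have an event and 60 × 0.7 = 42 are Holter-positive. Holter-only: (200 − 42)/200 = 79.0%. Any documented event: 140/200 = 70.0%. Gap: 9 points.

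Gap in percentage points over a range:

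| q | r = 20% | r = 30% | r = 40% |
|---|---|---|---|
| 0.3 | 14 | 21 | 28 |
| 0.5 | 10 | 15 | 20 |
| 0.7 | 6 | 9 | 12 |
| 0.9 | 2 | 3 | 4 |
| 1.0 | 0 | 0 | 0 |

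For scale, the 95% normal-approximation half-width at n = 200 is 1.96 × √(0.7 × 0.3/200) = 6.4 points for a rate of 70%. It runs from 4.2 points at 90% to 6.8 at 60%. The definitional gap can therefore be larger or smaller than sampling error, depending on q.

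**The case against.** The strongest reply is that Holter-only is what the sponsor meant. Section 4.2 and Appendix XII agree word for word, the Holter is scheduled once for everyone, and Sections 3.2 and 6.7 rest the bias control on its independent reading. That is a defensible endpoint and the intention is plausible. It still leaves the blanking clause in Section 4.2 without a function.

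A reader might infer that the plan states outright that recurrence after day 90 is a failure, so that the sections contradict each other. They do not go that far. Section 8.2.1 exempts early events and only implies that later ones count. Section 6.3.1 is a documentation standard placed under the pre-discharge visit, and Section 7.3.1 says which form records a recurrence. These lend support but do not define the endpoint.

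A reader might also infer that the Kaplan-Meier analysis has no event. That cannot be said. Parts of Section 8 are redacted and the table mockups are not shown; either may name it. Repeat ablation outside the blanking period (Section 4.3) is a natural candidate and would give the blanking rule in Section 8.2.1 a use. It would not explain the clause attached to the Holter definition itself.

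Three further inferences do not carry weight:
- Missing Holters are not left without a rule. Section 8.2.1 summarises what is available and Section 8.7 rules out imputation.
- Drug status is most naturally read at the 12-month visit, where Section 6.4.1 collects current use.
- "Atrial arrhythmias 30 seconds or longer will be collected" in Section 6.3.1 is a collection threshold before discharge, inside blanking, and differs from Section 4.2 only at exactly 30 seconds.

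**Conclusion.** The concern holds in a limited form. In the visible text, long-term success is defined by one 12-month Holter, the blanking period attached to it has no effect, and the analysis section implies a broader failure rule without stating it or naming the Kaplan-Meier event. Read literally, a documented recurrence or repeat ablation after day 90 followed by a clean Holter counts as a success.

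With complete Holters and simple proportions, the literal rate is equal to or higher than freedom from documented recurrence, by r(1 − q). That is 9 points at the assumed r = 30% and q = 0.7, and nothing at q = 1. No ordering is claimed outside those conditions, and none of these inputs comes from the documents. The conclusion also depends on the redacted parts of Section 8 and the mockups not already settling the matter.

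Separately, the repeat-ablation rate in Appendix XII is the complement of the one in Section 4.3, and its own label shows that *with* is meant.

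**What to change.** Reconcile Sections 4.2 and 8.2.1 and Appendix XII by reporting two labelled rates:

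- **(a) Freedom from documented recurrence.** The event is any AF/AFL/AT over the 30-second threshold documented after day 90 by any collected source. Name it in Section 8.2.1 as the Kaplan-Meier event, with the censoring already given there. State whether a repeat ablation for atrial arrhythmia after day 90 counts as an event.
- **(b) Point freedom at 12 months.** The core-laboratory Holter result among subjects who have one, without the blanking clause, reported with the number lacking a Holter.

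Use the same rhythm definitions for both drug-status versions in Section 4.2. If Holter-only is intended as the sole definition, say so, remove the blanking clause from it, and name what the Kaplan-Meier analysis measures. If redacted text already holds a rule, bring Section 4.2 and Appendix XII into line with it. In Appendix XII, change the repeat-ablation rate from *without* to *with*.

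The cost is wording, with no new visit or test. Sections 6.4.1, 6.5.1 and 6.6 already schedule collection of recurrence, other monitoring records and repeat ablation; the case report forms are under separate cover and could not be checked. The downside is that rate (a) may be lower. It also rests on recordings made only where applicable and not read by the core laboratory, so ascertainment will be uneven. That is the reason to keep rate (b) beside it.
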